2.2. Secondary Objectives

To determine efficacy of administration of increased dosage of eltrombopag to subjects with chronic ITP who did not respond to current maximally approved daily dose of 75 mg for at least 3 weeks by measuring: number of weeks of platelet counts of response; number of patients achieving a platelet count $> 100,000$, and number of platelet counts per patient $> 100,000$. (Note if a platelet count $> 100,000$ is achieved that week and the subsequent weeks of the 8 week study will be considered to all be over 100,000 for purposes of all analyses).

To determine efficacy of administration of increased dosage of eltrombopag to subjects with ITP who did not respond to current maximally approved daily dose of 75 mg for at least 3 weeks by measuring HRQoL and bleeding scores.

To determine the safety of administration of increased dosage of eltrombopag to subjects with ITP who did not respond to current maximally approved daily dose of 75 mg for at least 3 weeks.

To evaluate if there are subgroups of patients (despite this endpoint being underpowered) who are more likely or less likely to either respond or to experience adverse events based on:

[figure not shown]
Starting platelet counts, splenectomy status, concomitant meds e.g, daily prednisone at a maximum dose of 20mg daily, duration of ITP since diagnosis, starting Hemoglobin, WBC, and Absolute Neutrophil Count (ANC), starting ALTs, bilirubins or Alk Phos levels, Platelet Reticulocyte Count.

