Dose escalation will continue, despite satisfaction of the primary endpoint of study ($> 50,000$ and $> 20,000$ above baseline), until the platelet count reaches 100,000. The rationale for this approach is to maximize clinically relevant responses for the subjects and standardize data for analysis. Subjects will stop study medication if the platelet count is within the normal range, thereby minimizing any safety risk associated with elevated platelet count. By continuing to dose escalate subjects until the platelet count is $> 100,000$, the maximum response and correlation of dose will be tracked allowing better understanding of sustained response and dose-dependent response, which can be applied to future consideration dosage for periods of short-term hemostasis (i.e surgical procedures). The 8 weeks of data collected in enrolled subjects on the standardized

protocol will have the balance of consistency of dosage and unequivocality of response while maintaining subject safety.

If agreed on by the P-I, subjects may obtain local counts or see their local hematologist for study visits. All study-required procedures will be faxed to the P-I for review. The appropriate dosing adjustments will be determined by the P-I.

According to the new consensus guidelines (Provan Blood, 2009), male and female subjects with > 1 year duration of ITP are diagnosed with chronic ITP. Enrollment began with adult subjects \geq 18 years of age, and was extended to include pediatric patients $>$ 12 years of age after a review of this unblinded safety information by the independent Data Safety Monitoring Officer (DSMO). Additionally, we will now allow the inclusion of pediatric patients \geq 3 year of age to enroll on the protocol. The rationale for treating patients on this study is to allow people to be successfully treated and thus increase their platelet count by using a higher dose of eltrombopag when they do not respond to 75 mg daily of eltrombopag. Since some children do not respond to 75mg, the rationale and the dosing (when and how to increase) would be the same.

Long Term Treatment Extension (Part 2): (48 months)

After 8 weeks or once dosing is stopped because the platelet count is $>100,000$, the subject will be unblinded, once the data forms are complete with the assistance of the research pharmacy.

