Subjects who received and responded to eltrombopag higher dose treatment will have the option to continue therapy with periodic monitoring and ongoing dose adjustment on the open-label extension study.

Subject who had a platelet count $> 100,000$ can enter Part 2 at the dose at which the subject met primary response criteria after the platelet count decreases to $< 100,000$ /uL on serial monitoring in the immediate post-study monitoring period.

Subjects randomized to the placebo group who did not respond will have the opportunity to receive open label escalated dose eltrombopag over 8 weeks following the study protocol as if they had been randomized to active drug in the study. This group will provide the “confirmatory group” to see if the rate of response in the randomized group can be confirmed in this group.

Consent will be obtained for additional monitoring with bone marrow aspirate and biopsy at 1 year (at year 2, year 3, year 4) and additional ophthalmologic examinations for cataracts at 6 months and 18 months.

It is considered standard of care to monitor all patients as possible who have been on eltrombopag treatment for 1 year because of the higher doses of eltrombopag administered in this protocol. All subjects will have bone marrow aspiration/biopsies for their clinical care, no bone marrows will be performed for research purposes only.

Optional PK sampling will be done 4 weeks after the subject has been on active study drug (or at another time point if this is not convenient). There will be 3 samples drawn: the 1st sample will be drawn prior to taking the study drug for that day, the 2nd PK sample will be drawn 2-4 hours after the dose was taken and the 3rd sample will be drawn 5-8 hours after the dose was taken. These PK tests are being done to measure how much eltrombopag is in the blood at various time points following administration of eltrombopag and can be compared to published data.

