At Enrollment: (Part 1)

CBC with Differential
Reticulocyte Count
Peripheral Smear
CMP (Sodium, Potassium, Bicarbonate, Chloride, BUN, Creatinine, Glucose, Calcium, Total Protein, Albumin, including AST/ALT, Fractionated Bilirubin Level)
Platelet Reticulocyte Count
Eye Examination for caratacts
History, Physical with Vital Signs and Bleeding Score
HRQOL

Every 2 Weeks until week 8:

Reticulocyte count, Platelet Reticulocyte count
Peripheral Smear (if indicated)
CMP
History, Physical with Vital Signs and Bleeding Score

Long Term Treatment Extension: (Part 2)

Performed at each study visit:

CBC with Differential platelet count, Reticulocyte count, Platelet Reticulocyte count
Peripheral Smear (if indicated)
History, Physical with Vital Signs

After the end of treatment during the dose escalation phase, all subjects can be monitored at 4 weeks intervals and then can go to every 8 weeks for the remainder of the study at the discretion of the investigator (investigator may require subjects to come in for additional monitoring if deemed necessary).

After 6 months on therapy:

Eye Examination

After 12 months on therapy:

Bone Marrow Aspirate and Biopsy
HRQOL

After 18 months on therapy:

Eye Examination

After 24 months on therapy

Bone Marrow Aspirate and Biopsy

*Please Note: A bone marrow aspiration/biopsy will only be performed at 24 months if the subject's reticulin fibrosis grade is a 2 or 3 during the 12 month procedure.
HRQOL

After 36 Months on therapy

Bone Marrow Aspirate and Biopsy

*Please Note: A bone marrow aspiration/biopsy will only be performed at 36 months if the subject's reticulin fibrosis grade is a 2 or 3 during the 24 month procedure.

HRQOL

After 48 Months on therapy

Bone Marrow Aspirate and Biopsy

*Please Note: A bone marrow aspiration/biopsy will only be performed at 48 months if the subject's reticulin fibrosis grade is a 2 or 3 during the 36 month procedure.

HRQOL

Post Study Period after completion of dosing

Weekly

CBC with Differential platelet count, Reticulocyte count, Platelet Reticulocyte count
Peripheral Smear (if indicated)

History, Physical with Vital Signs and Bleeding Score
HRQOL (Week 1 – End of 8 Week Blinded study/ End of Extension Study)

Every 2 Weeks until week 4:
CMP
History, Physical with Vital Signs and Bleeding Score

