6.1. Critical Baseline Assessments

Screening to ensure subject eligibility criteria will occur within 30 days prior to administration of study medication. Screening assessments will include CBC, CMP (Sodium, Potassium, Bicarbonate, Chloride, BUN, Creatinine, Glucose, Calcium, Total Protein, Albumin, including AST/ALT, Fractionated Bilirubin Level), D-Dimer and urine pregnancy test (for women of childbearing potential).

6.2. If subject meet all other criteria for enrollment, a baseline ophthalmologic examination will be performed within 2 weeks of administration of study medication.

6.3. Primary Response Criteria:

Complete Response (CR) will be defined as a 2 consecutive platelet counts $\geq 50,000 / \mu\text{L}$ AND $> 20,000$ more than the baseline platelet count at enrollment within the 8 week increased dose window not as a result of rescue treatment. Partial Response (PR) will be defined as a 2 consecutive platelet counts $\geq 50,000 / \mu\text{L}$ OR $> 20,000$ more than the baseline platelet count at enrollment within the 8 week increased dose window not as a result of rescue treatment.

For uniformity of dosing and data analysis and for better understanding of increased dose effects, patients randomized to the treatment arm will automatically take:

- 100 mg for 2 weeks
- 125 mg for 2 weeks
- 150 mg for 4 weeks

However, if the platelet count increases to $\geq 100,000 / \mu\text{L}$, study drug will be interrupted and will not be resumed until platelet count is below 100,000 / μL and the patient desires to enroll on the Part 2 long term treatment extension study. The patient will finish with the Part 1 of the study at this point but can enter Part 2 the long term treatment extension study at dose at which the patient met primary response criteria, after the platelet count decreases to $< 100,000 / \mu\text{L}$ on serial immediate post-study monitoring period.

Rescue treatment will be defined as new treatment for chronic ITP eg IV anti-D or IVIG, an increased dose of steroids, or platelet transfusion. Use of rescue treatments will be allowed, but patients will be regarded as non-responders for the duration of rescue treatment and until 2 weeks beyond.

Secondary Response Criteria:

-Platelet Count $\geq 50,000$ and $> 20,000$ above baseline for at least 3 of the last 4 of 8 weeks independent of rescue therapy

- Platelet Count \geq 50,000 /uL and $>$ 20,000 above baseline for any 4 of 8 weeks independent of rescue therapy

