- At least One Platelet count \geq 100,000
- Number of weeks with Platelet Counts \geq 50,000 /uL and $>$ 20 from baseline in 8 Weeks reduction of bleeding score from baseline to the last count of the study improvement of HRQoL
- Number of weeks with Platelet Counts $>$ 100,000 in 8 Weeks

Secondary Efficacy Endpoints:

- Dose required achieving first platelet count \geq 50,000 /uL and $>$ 20 from baseline
- Average Platelet Count at each dose level
- Bleeding scores using WHO score
- Use of Rescue Treatments

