10. APPENDICES

10.1. Appendix 1

Attached Table 1: Study Assessments and Procedures

| Part 1 | Screen < 28 days | Day 1 | Week 2 | Week 4 | Week 6 | Week 8 |
|-------------------------------------------|------------------|-------|--------|--------|--------|--------|
| Written Informed Consent | X | | | | | |
| Inclusion/Exclusion Criteria | X | | | | | |
| Demographics | X | | | | | |
| Register | X | | | | | |
| Eye Exam | X | | | | | |
| Pregnancy Test * | X | | | | | |
| Randomization | X | | | | | |
| History and Physical (Vital Signs) | | X | X | X | X | X |
| Bleeding Score | | X | X | X | X | X |
| HRQOL | | X | | | | |
| CBC | X | X | X | X | X | X |
| Reticulocyte | X | X | X | X | X | X |
| Platelet Reticulocyte | X | X | X | X | X | X |
| Peripheral Smear* | X | X | X | X | X | X |
| CMP | X | X | X | X | X | X |

| Part 2 | 6 Month | 12 Month | 18 Month | 24 Month | 30 Month | 36 Month | 42 Month | 48 Month |
|--------------------------------|---------|----------|----------|----------|----------|----------|----------|----------|
| Eye Exam | X | | X | | | | | |
| Bone Marrow Examination | | X | | X** | | X** | | X** |
| HRQOL | | X | | X | | X | | X |
| CBC | | | | | | | | |
| Reticulocyte | | | | | | | | |
| Platelet Reticulocyte | | | | | | | | |
| Peripheral Smear * | | | | | | | | |
| CMP | | | | | | | | |

*If clinically indicated

** Bone marrow aspirations/biopsies will be performed annually depending on the reticulin fibrosis grade of the bone marrow performed at year 1. A bone marrow

aspiration/biopsy will be repeated the next year if the subject's reticulin fibrosis grade is a 2 or 3.

| Post Study Period | Week 1 | Week 2 | Week 3 | Week 4 |
|------------------------------|---------------|---------------|---------------|---------------|
| CBC | X | X | X | X |
| Reticulocyte | X | X | X | X |
| HRQ0L | X | | | |
| Platelet Reticulocyte | X | X | X | X |
| Peripheral Smear * | X | X | X | X |
| CMP | X | | X | |

10.2 Appendix 2

PHARMACOKINETIC SAMPLING

PK Sample Collection

After a minimum of 4 weeks on active study drug, 2mL blood samples for PK analysis will be collected in K2 EDTA-containing tubes. One sample will be collected at each of the following times: within 1 hour prior to eltrombopag dosing (pre-dose sample), and at 2- 4 hours and 5-8 hours after eltrombopag dosing.

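### HRQoL is not measured during blinded dosing after Day 1; the only near follow-up comes after dosing ends, when the blind may be broken or treatment changed

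*Combined protocol and SAP*

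**What the plan says.** Section 2.2 makes HRQoL part of a secondary efficacy objective, to be met "by measuring HRQoL and bleeding scores". The secondary response criteria in section 6.3, repeated in section 8.3.1.1, run it into the bleeding-score item: "reduction of bleeding score from baseline to the last count of the study improvement of HRQoL". HRQoL is given no time point of its own, so only the visit schedule decides which values exist.

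In Part 1 the schedule gives HRQoL at enrolment (section 3.1) or Day 1 (Appendix 1) and at no later visit. The next assessment is in a list headed "Post Study Period after completion of dosing", where it reads "HRQOL (Week 1 – End of 8 Week Blinded study/ End of Extension Study". The Appendix 1 post-study table also marks it in week 1. In Part 2 it recurs at 12, 24, 36 and 48 months.

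Three other rules govern what happens around the end of Part 1:

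- Early stop (section 6.3): at a count of 100,000 or more, "study drug will be interrupted and will not be resumed until platelet count is below 100,000".
- Unblinding (section 3.1, Part 2): after 8 weeks or an early stop, "the subject will be unblinded, once the data forms are complete with the assistance of the research pharmacy".
- Cross-over (section 3.1, Part 2): "Subjects randomized to the placebo group who did not respond will have the opportunity to receive open label escalated dose eltrombopag over 8 weeks".

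**The concern.** HRQoL is self-reported, so the answers can shift once a subject knows which treatment was given. The randomized comparison protects such an outcome only if it is recorded while the blind holds, and it describes the effect of the higher dose only if it is recorded while that dose is being taken. Here the only follow-up value near the blinded phase is taken after both conditions may have lapsed.

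If so, a difference between arms, or its absence, could reflect knowledge of assignment, a stop in dosing or the start of open-label drug. The HRQoL part of the section 2.2 objective would then have no assured blinded, on-treatment comparison behind it.

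**Working it through.** The plan gives no figure for HRQoL to reproduce, so the check sets the schedules beside the rules for stopping, unblinding and cross-over.

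**1. What Part 1 collects (Appendix 1).**

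| Measure | Day 1 | Week 2 | Week 4 | Week 6 | Week 8 |
|---|---|---|---|---|---|
| HRQoL | X | – | – | – | – |
| Bleeding score | X | X | X | X | X |

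Post-baseline Part 1 visits with HRQoL: 0 of 4. With the bleeding score, which shares the objective: 4 of 4 ("Bleeding Score | | X | X | X | X | X"). The visit lists in section 3.1 agree: HRQoL is listed at enrolment and is absent from the two-weekly list to Week 8. The gap therefore appears in two places and is not a stray blank in one table.

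**2. When the next form falls.** It is due in post-study week 1. If dosing stops at a visit in week w, that is about study week w + 1:

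| Dosing stops at week | 2 | 4 | 6 | 8 |
|---|---|---|---|---|
| HRQoL at about week | 3 | 5 | 7 | 9 |

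A stop before Week 8 can be triggered by the platelet count, so the timing of the form depends on response. Section 8.2.1 assumes response in 50% of the active arm and 5% of the placebo arm. Those rates refer to the lower response threshold and not to reaching 100,000, so they do not give the share of early stops. They do suggest that timing would differ by arm.

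**3. The subject's state at that form.**

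- *Off drug.* This follows from the early-stop rule for subjects who reached 100,000, unless the count has already fallen and they have entered Part 2. For Week 8 completers the heading of the list points the same way, but the documents do not describe their treatment in that week.
- *Unblinded.* Unblinding waits for completed data forms. Nothing says the post-study HRQoL form is among them, so it may come before or after.
- *On open-label drug.* No waiting period precedes cross-over. Section 8.3.1 notes that placebo subjects will have had at least 11 weeks on 75 mg when they start escalation. The run-in is at least 3 weeks and Part 1 lasts 8, and 3 + 8 = 11, which leaves room for no gap after Week 8.

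These are alternatives for different subjects and need not occur together. There is also a fourth possibility: a subject who crosses over at once may have no post-study week 1 at all. The next scheduled HRQoL would then be the 12-month form, and the follow-up value for the blinded phase would be missing.

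**The case against.** The strongest reply starts from the label, which ties the form to the end of the 8-week blinded study. Unblinding waits for the data forms, and section 5.5 places cross-over after unblinding. If the HRQoL form is one of those data forms, it precedes both events and the blind holds. On that reading the fault is an unstated order of events, not a demonstrated loss of blinding. A subject already on open-label drug also fits poorly under a heading about the time after dosing.

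This is fair as far as it goes: loss of the blind and open-label exposure are possibilities that the documents leave open. But no section says that the form comes first, and Appendix 1 marks post-study week 1 while leaving Week 8 blank. Even if the form does come first, it is still taken off drug in subjects stopped at 100,000.

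A second reply is that the stakes are modest. Section 8.3.1 calls secondary analyses underpowered and descriptive. No instrument, recall period or between-arm HRQoL test is specified, so one cannot say how badly a form taken about a week late represents the treatment period. This limits the weight of the point but does not remove it, since a descriptive comparison of arms also needs values taken under like conditions.

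A third reply is that taking the form at the last Part 1 visit still leaves early stoppers assessed sooner than the rest. That is correct, and it remains after the fix.

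**Conclusion.** The concern holds. Followed as written, the plan schedules no follow-up HRQoL value that is both blinded and on treatment, and this applies to every subject. The absence of an HRQoL form at all 4 post-baseline Part 1 visits is certain. That the post-study form may follow unblinding or a change of treatment rests on the documents' silence about the order of events.

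The size of any bias cannot be derived, because the documents give no HRQoL instrument or expected values. The effect is confined to one secondary, descriptive measure; the primary endpoint rests on platelet counts and is unaffected. The sponsor should make the change because it is cheap and removes a clear weakness in a self-reported outcome.

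**What to change.** In section 3.1 and Appendix 1, schedule HRQoL at Week 8, or at the last Part 1 visit if dosing stops early. State that the form is completed before unblinding and before any Part 2 drug. In sections 6.3 and 8.3.1.1, separate HRQoL improvement from the bleeding-score item and define it as the change from Day 1 to that visit. Because early stoppers will be assessed at Week 2, 4 or 6, report the assessment week by arm beside the HRQoL results.

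The cost is one questionnaire at an existing visit, or moving the week 1 form about a week earlier. Dosing and sample size do not change. Subjects who have already completed Part 1 will lack the value. Report their post-study forms separately, with treatment and blinding status at completion where these were recorded.

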4. SUBJECT SELECTION AND WITHDRAWAL CRITERIA

4.1. Number of Subjects:

60 subjects will be enrolled.

4.2. Inclusion Criteria:

Subject or their parent/ guardian has signed and dated a written informed consent

Males and Females aged 3 year or older, who can swallow a tablet, and are diagnosed with chronic ITP according to the new consensus guidelines (Provan, Blood, 2009) are eligible.

No indication of a disease which may cause thrombocytopenia other than ITP---- no specific testing required

Subjects with thrombocytopenia $\leq 50,000 /uL$ after at least 21 days of daily dosage with eltrombopag 75mg

Stable dosage of concomitant treatments for ITP
 ≥ 2 weeks or longer (corticosteroids);

At least 2 weeks from rescue therapy for ITP (WinRho, IVIG, corticosteroids, platelet transfusion) or 1 week if therapy has clearly been ineffective

At least 4 weeks from rituximab treatment

Pregnant or Lactating Women are excluded

Women of child-bearing age with a negative pregnancy test within 7 days of enrollment and who agree to use acceptable methods of birth control will be eligible for this study

Female subjects or female partners of male subjects must either be of non-child bearing potential (hysterectomy, bilateral oophorectomy , bilateral tubal ligation or post menopausal for more than one year) OR, if of child bearing potential, using one of the following highly effective methods of contraception.
-complete abstinence from intercourse

- Intrauterine device (IUD)
- Two forms of barrier contraception. diaphragm plus spermicide, or for males condoms plus spermicide.
- Male partner is sterile and is the only partner of the female.
- Systemic contraceptives

4.3. Exclusion Criteria:

Previous history of eltrombopag-related LFT elevation that required sustained interruption of treatment

Previous history of immediate or delayed hypersensitivity reaction or idiosyncrasy to drugs chemically related to eltrombopag

Known HIV Infection

History of Arterial or Venous Thrombosis within the past year or requiring ongoing therapy

Known Active Hepatitis C infection

Elevated AST/ALT or Creatinine > 1.5 times upper limit of normal in 4 weeks prior to enrollment*

Abnormalities in WBC, ANC and Hemoglobin > 1.5 times upper or lower limit of normal*

* Subjects can be rescreened to be included

4.4. Withdrawal Criteria:

Subject may withdraw consent at any time

Adverse event that would in the investigators judgement, make continued participation in the study an unacceptable risk

Development or diagnosis of new thrombotic event

Development of new onset clinically significant ocular changes related to cataracts on serial ophthalmologic examination

Development of MF3 fibrosis on bone marrow examinations

Development of Drug Induced Liver Injury necessitating sustained interruption of study drug

Please see Liver Chemistry Stopping and Follow up Criteria (see 6.3.1)

